6.3.2 Prohibited Concomitant Medications

Subjects are prohibited from receiving the following therapies during the Screening and Treatment Period of this study:

- Antineoplastic systemic chemotherapy or biological therapy
- Immunotherapy not specified in this protocol
- Chemotherapy not specified in this protocol
- Investigational agents other than talimogene laherparepvec
- Radiation therapy (Note: Radiation therapy to a symptomatic solitary lesion may be allowed with the approval of the Lead PI.)
- Live vaccines within 30 days prior to the first dose of study drug and while participating in the study. Examples of live vaccines include, but are not limited to, the following: measles, mumps, rubella, varicella/zoster, yellow fever, rabies, BCG, and typhoid vaccine.
- Systemic immunosuppressive therapy within 2 weeks including oral steroid doses > 10 mg/day of prednisone or equivalent within 7 days prior to enrollment.
- Antiherpetic drugs such as acyclovir. Intermittent topical use is permitted.

Subjects who, in the assessment by the Investigator, require the use of any of the aforementioned treatments for clinical management should be removed from the trial. Subjects may receive other medications that the Investigator deems to be medically necessary.

There are no prohibited therapies during the Follow-up Period.

7.0 DOSE MODIFICATION AND TOXICITY MANAGEMENT

Subjects will be monitored continuously for AEs throughout the study and for 30 days after the last dose of study drug. Subjects will be instructed to notify their treating physician of any and all AEs. Toxicity will be graded according to NCI-CTCAE version 5.0.

All AEs should also be managed with supportive care at the earliest signs of toxicity considered related to study drug(s).

7.1 Dose Modifications

Subjects experiencing one or more AEs due to the study drug may require dose modification(s) as described in Table 7.1. If talimogene laherparepvec treatment was delayed by > 1 week, that dose will be deemed to have been missed and the subject will proceed to the next scheduled treatment visit. Missed doses will not be made up. If talimogene laherparepvec dosing is delayed by more than 4 weeks from the date of the planned dose (i.e., approximately 6 weeks from the previous dose) due to the occurrence of an adverse event that is considered related to talimogene laherparepvec, the subject must be permanently taken off talimogene laherparepvec treatment. If talimogene laherparepvec is delayed by more than 4 weeks from the date of the planned dose (i.e., approximately 6 weeks from the previous dose) for reasons other than treatment-related toxicity, the case must be reviewed by the PI to determine if the subject can resume talimogene laherparepvec therapy.

Table 7.1 Talimogene Laherparepvec Dose Modifications

HEMATOLOGIC ADVERSE EVENTS		
Toxicity Grade ^a	Occurrence	Talimogene Laherparepvec
NEUTROPENIA		
Grade 1	Any	Maintain dose
Grade 2	Any	Maintain dose
Grade 3($\geq 0.5 - < 1 \times 10^9/L$)	1 st	Hold until grade ≤ 1 , then resume at current dose
	2 nd and higher	Hold until grade ≤ 1 , then resume at 80% of current dose ^d
Grade 4 ($< 0.5 \times 10^9/L$)	1 st	Hold until grade ≤ 1 , then resume at 80% of current dose. ^{b,c,d}
	2 nd and higher	Hold until grade ≤ 1 , obtain permission of PI to resume at 60% of current dose ^d
FEBRILE NEUTROPENIA		
Grade 3 (neutropenia and fever $\geq 38.5C$)	1 st – 2 nd	Hold until resolution of fever and neutropenia to grade ≤ 1 , then resume at 60% of current dose ^d
	3 rd	Discontinue Protocol Therapy
Grade 4 (neutropenia and fever $> 38.5 C$)	Any	Discontinue Protocol Therapy

- a. National Cancer Institute Common Terminology Criteria Version 3.0
- b. Continued treatment only if it is considered to be in the best interest of the patient
- c. Consider growth factor support if continuing treatment is felt to be in the patient's best interest.
- d. **NOTE:** After Cycle 1, at the discretion of the treating physician, once there is recovery of the toxicity to grade ≤ 1 , the treating physician may choose, to hold oxaliplatin and continue capecitabine and pembrolizumab at current dose as clinically indicated. If the treating physician chooses to restart oxaliplatin later in the patient's treatment course, the dose of oxaliplatin at which the patient restarts should be one dose level lower than last dose level on which patient was treated. The specific treatment approach used and dose modifications that occur are required to be reported in the Case Report Forms.

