3.2.1 Dose Limiting Toxicity

Toxicity should be evaluated and defined according to CTCAE version 5.0, and should only include events assessed as related to talimogene laherparepvec during treatment and up to 30 days after the last talimogene laherparepvec injection.

The following herpetic events should be considered as DLTs:

- Serious herpetic events such as herpetic encephalitis, encephalomyelitis or disseminated hepatic infection.
- Any herpetic events confirmed due to talimogene laherparepvec that require treatment with acyclovir or similar anti-viral agent. Talimogene laherparepvec treatment should be suspended if treatment is required with systemic acyclovir or other anti-virals. If ongoing anti-viral treatment is required, talimogene laherparepvec treatment should be permanently discontinued.

The following are also considered DLTs:

- Grade 3 or greater immune-mediated adverse events.
- Any grade plasmacytoma at or near the injection site or evidence of impaired wound healing at the injection site.
- Grade 3 or greater allergic reactions considered at least possibly related to talimogene laherparepvec.
- Grade 4 non-hematologic toxicity.
- Grade 3 non-hematologic toxicity lasting > 3 days despite optimal supportive care;
 - Grade 3 fatigue will not be classified as DLT, irrespective of duration.
- Any Grade 3 or higher non-hematologic laboratory value if:
 - Medical intervention is required, or
 - The abnormality leads to hospitalization, or
 - The abnormality persists for > 1 week unless deemed not clinically important per both treating physician and study PI or co-PI.
- Grade 3 or 4 febrile neutropenia.
- Grade 4 thrombocytopenia associated with bleeding event required intervention.
- Any other intolerable toxicity leading to permanent discontinuation of talimogene laherparepvec.
- Grade 5 toxicity (i.e., death).

If an unexpected DLT occurs, talimogene laherparepvec administration should be delayed until the DLT has resolved to at least CTCAE (v. 5.0) Grade 1. If talimogene laherparepvec dosing is delayed by more than 6 weeks from the date of the planned dose due to the occurrence of an adverse event that is

considered related to talimogene laherparepvec, the subject must be permanently taken off talimogene laherparepvec treatment.

Management and dose modifications associated with all adverse events are outlined in Section 7.0.

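### Sections disagree on when a subject must stop study drug (delay limit, antiviral use), and DLT evaluability does not require the Day 22 cohort dose

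*Combined protocol and SAP*

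**What the plan says.** **Delay.** Section 7.1 takes a subject permanently off drug for a delay due to a related adverse event, under a sentence that begins "If talimogene laherparepvec dosing is delayed by more than 4 weeks from the date of the planned dose". It glosses this limit as about 6 weeks from the previous dose. Section 3.2.1 has the parallel sentence "If talimogene laherparepvec dosing is delayed by more than 6 weeks from the date of the planned dose due to the occurrence" of a related adverse event, also ending in permanent discontinuation. It then adds: "Management and dose modifications associated with all adverse events are outlined in Section 7.0". Section 7.1 also provides that after a delay of more than 1 week "that dose will be deemed to have been missed and the subject will proceed to the next scheduled treatment visit", and that missed doses are not made up.

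**Systemic antivirals.** One DLT bullet in Section 3.2.1 is "Any herpetic events confirmed due to talimogene laherparepvec that require treatment with acyclovir or similar anti-viral agent". The same bullet continues "Talimogene laherparepvec treatment should be suspended if treatment is required with systemic acyclovir or other anti-virals" and "If ongoing anti-viral treatment is required, talimogene laherparepvec treatment should be permanently discontinued". Section 6.3.2 lists as prohibited during screening and treatment "Antiherpetic drugs such as acyclovir. Intermittent topical use is permitted", and says that a subject who needs a listed treatment should be removed from the trial. Section 6.3 is softer: discontinuation may be required, and questions go to the Lead PI.

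**DLT evaluability.** Section 3.1 counts an escalation subject as evaluable for DLT if the subject was accrued, received study treatment and completed the first cycle of safety assessments, or had a treatment-related DLT that prevented completion. It does not mention the Day 22 dose. Under Table 3.1 everyone receives 4×10^6 PFU on Day 1, and the first dose at the assigned level comes three weeks later.

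**The concern.** The first two items are instructions to sites. This trial uses external sites, and a site working from Section 3.2.1 could give a dose that Section 7.1 bars, after a related toxicity has kept the subject off drug for more than four weeks. A site treating a confirmed drug-related herpetic event could either pause dosing or take the subject out of the trial, and could cite the protocol for each.

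The third item bears on the primary safety result. Escalation is decided on DLTs among evaluable subjects over the first five weeks. A subject can attend every Cycle 1 visit, miss Day 22 and have no DLT. That subject meets the Section 3.1 definition and enters the count as a clean result for a level never received. If this happened to one of three subjects at Level 2 or 3, a finding of no DLT in three would rest on two subjects exposed at that level.

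**Working it through.** **1. The plan's own figure.** Section 7.1 equates 4 weeks from the planned dose with about 6 weeks from the previous dose. With the 2-week interval, 2 + 4 = 6 weeks, so the gloss is reproduced. For the Day 22 dose, which follows Day 1 by three weeks, it is 3 + 4 = 7 weeks. The Section 3.2.1 limit measured the same way is 2 + 6 = 8 weeks, or 3 + 6 = 9 weeks for Day 22. The limits therefore differ by two weeks from either anchor.

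**2. Where the limits disagree.** Cycle 1 lasts five weeks and later cycles two, so cohort doses fall on Days 22, 36, 50 and 64. A dose delayed by more than 1 week is missed and dosing moves to the next visit, so a prolonged hold ends on one of these days. Delay is the resumption day minus the day of the first held dose. Section 7.1 bars a delay over 28 days and Section 3.2.1 one over 42 days. The range applies the ±3-day window to the resumption visit.

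| Held from | Resumed | Nominal delay (days) | Range | Barred by 7.1 | Barred by 3.2.1 |
|---|---|---|---|---|---|
| 22 | 36 | 14 | 11–17 | no | no |
| 22 | 50 | 28 | 25–31 | only above 28 | no |
| 22 | 64 | 42 | 39–45 | yes | only above 42 |
| 36 | 50 | 14 | 11–17 | no | no |
| 36 | 64 | 28 | 25–31 | only above 28 | no |
| 50 | 64 | 14 | 11–17 | no | no |

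On nominal days one pair of six differs: Day 22 to Day 64. At the late edge of the window two more differ: Day 22 to Day 53 (53 − 22 = 31) and Day 36 to Day 67 (67 − 36 = 31). Day 22 to Day 67 (45 days) is barred by both. If instead each missed visit restarts the count, neither limit is reached.

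**3. Antivirals side by side.** For a herpetic event confirmed as due to the drug and needing a systemic antiviral:
- Section 3.2.1: it is a DLT; suspend study drug; stop permanently only if the antiviral is ongoing.
- Section 6.3.2: remove the subject, with no exception for a short course.

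The event counts as a DLT whichever instruction is followed. What differs is whether the subject may resume dosing and stay in the trial.

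**4. Evaluability without the cohort dose.** This route does not depend on antivirals:
- Table 7.1 holds drug for Grade 3 or 4 neutropenia until it recovers to Grade 1 or better.
- Section 3.2.1 lists febrile neutropenia as a DLT but not neutropenia without fever.
- If the hold covers Day 22 and lasts over a week, that dose is missed and the next visit is Day 36, after Cycle 1.
- The subject can still complete the Cycle 1 assessments and so is evaluable under Section 3.1.

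Day 1 dose as a fraction of the cohort dose:
- Level 1: 4×10^6 / 4×10^6 = 1
- Level 2: 4×10^6 / 4×10^7 = 1/10
- Level 3: 4×10^6 / 4×10^8 = 1/100

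**The case against.** **Delay.** Stopping at 4 weeks satisfies both sections, Section 3.2.1 points to Section 7.0 for management, and the Section 7.1 gloss suggests that 6 weeks from the previous dose became 6 weeks from the planned dose by a slip. All of that is fair and makes the repair easy. It does not settle the conflict, because the pointer does not say that Section 7.0 prevails. Nor can the 6-week rule be read as one for DLTs only: it follows a sentence about unexpected DLTs, but its own trigger is any related adverse event.

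**Antivirals.** A reader might infer that the choice between suspending and removing a subject changes who is DLT-evaluable. The documents do not support that. The suspension sentences sit inside the bullet for confirmed drug-related events, which are already DLTs. For other herpetic events the natural reading is that Section 6.3.2 applies, with questions going to the Lead PI. A reader might also infer that removal ends safety follow-up. It need not: Sections 7.0 and 10.1 carry adverse event monitoring to 30 days after the last dose, Section 5.3 moves a subject into follow-up after the last dose, and Appendix C (note 2) requires the 30-day visit for all subjects.

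**Evaluability.** Section 3.1 uses the word any for the toxicity and efficacy populations and omits it for DLT, which hints that more than the seroconversion dose is meant. The PI, co-PI and study chair also review the data before escalation from the first level and could discount such a subject. But a dropped word is not a dose requirement, and Section 10.5 has the reviewers apply the rules in Section 3.2, which contain none. The objection does have force at Level 1, where the Day 1 dose equals the cohort dose and the missing information is a second administration rather than a higher dose.

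**Conclusion.** Three wording defects stand, all minor.

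1. The delay limits conflict. The reach is one of six hold-and-resume pairs on nominal days and three of six once the ±3-day windows are allowed. This assumes that delay is counted from the first held dose.
2. The antiviral instructions conflict for herpetic events confirmed as due to the drug. DLT status is unaffected.
3. DLT evaluability does not require the cohort dose. This matters most for the result, because at Levels 2 and 3 a subject exposed to 1/10 or 1/100 of the dose can count as a clean observation.

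A reader might go further and conclude that the 3+3 rules or the sample size are wrong. Nothing here shows that. The third item concerns who enters the count, not the counting rule. How often Day 22 would be missed without a DLT cannot be estimated from the documents, which give no rate for such holds with intraperitoneal dosing.

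**What to change.** - **Section 3.2.1:** change the limit to more than 4 weeks from the planned dose, matching Section 7.1. State that delay is counted from the first held dose, if that is the intention.
- **Section 6.3.2:** for herpetic events confirmed as due to the drug, refer to Section 3.2.1 (suspend; discontinue if the antiviral is ongoing). No new follow-up is needed.
- **Section 3.1:** make DLT evaluability in the escalation cohort conditional on receiving the Day 22 cohort dose or having a DLT, and replace subjects with neither. Table 3.1 already counts evaluable subjects, so replacement fits the design. A single rule for all levels is simplest, although the argument is weaker at Level 1.
- **Table 7.1, tidy-up only:** footnote a should cite CTCAE version 5.0. Footnote d should lose its text on oxaliplatin, capecitabine and pembrolizumab, which are not used here, and keep its last sentence on CRF reporting.

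The cost is an amendment to wording, plus one replacement enrolment for each escalation subject who misses Day 22 without a DLT.

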9.1.2 Primary Endpoint

The primary objective of the study is to define the safety and toxicity profile of talimogene laherparepvec in patients with peritoneal surface dissemination from gastrointestinal, fallopian tube, ovarian, or primary peritoneal tumors. The MTD across three dose levels will be determined as described in Table 3.1. The safety analyses will be performed on the safety population, as defined above. Incidence of adverse events occurring in 10% or more of patients will be summarized by Grade, overall and by dose level.

Adverse events will be described using the NCI CTCAE 5.0 criteria. Frequency and severity of adverse events according to the NCI CTCAE v 5.0 body system and severity criteria will be described. In addition, frequency of Grade 3 or 4 adverse events will be described separately. Causality will also be noted.

Laboratory assessments will also be described according to the NCI CTCAE criteria, with separate descriptions for Grade 3 or 4 laboratory abnormalities. Clinically significant laboratory abnormalities will be described as well. Serious adverse events will be summarized, including a causality assessment.

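### Table 7.1 carries a footnote on three drugs this trial does not give, cites CTCAE version 3.0 instead of 5.0, and prints overlapping febrile-neutropenia criteria that lead to different actions

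*Combined protocol and SAP*

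**What the plan says.** Section 7.1 sends subjects with adverse events due to the study drug to Table 7.1, which by its title covers talimogene laherparepvec alone. Three parts of that table matter here.

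- **Footnote d.** After Cycle 1 and recovery of the toxicity, the treating physician may "hold oxaliplatin and continue capecitabine and pembrolizumab at current dose as clinically indicated". A rule for restarting oxaliplatin one dose level lower follows, then a sentence on recording dose modifications in the case report form. Section 6.3.2 lists "Antineoplastic systemic chemotherapy or biological therapy" among the therapies barred during screening and treatment, together with any immunotherapy the protocol does not specify.
- **Footnote a.** The toxicity-grade column is tied to "National Cancer Institute Common Terminology Criteria Version 3.0". Section 7.0, directly above, says "Toxicity will be graded according to NCI-CTCAE version 5.0", and Section 9.1.2 says "Adverse events will be described using the NCI CTCAE 5.0 criteria". The synopsis, Section 3.2.1 and Section 5.6 also name version 5.0.
- **Febrile-neutropenia rows.** One row begins "Grade 3 (neutropenia and fever" and gives a threshold of ≥38.5 °C. The other begins "Grade 4 (neutropenia and fever" and gives >38.5 °C. For a first or second Grade 3 event the action begins "Hold until resolution of fever and neutropenia to grade" ≤1 and ends with resumption at 60% of the current dose. A third Grade 3 event, or any Grade 4 event, ends protocol therapy.

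**The concern.** A dose-modification table should lead from one event to one action, using the scale on which the rest of the trial grades toxicity. This table falls short in three ways. Every reduced-dose cell points to text that cannot be applied. The grading version differs from the one used for DLTs and for the primary safety analysis. And the two febrile-neutropenia criteria overlap while their actions differ.

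The third point has a consequence for patients. The protocol allows external sites (Section 3.1). On the same event, one site could resume the virus at 60% and another could stop it. That affects both the patient's treatment and the exposure recorded at that dose level, in a trial whose primary objective is the toxicity profile.

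**Working it through.** The plan states no figure to reproduce on this point. The check compares texts and then does simple dose arithmetic.

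**Footnote d.** The table has nine action cells: neutropenia Grade 1, Grade 2, Grade 3 first, Grade 3 second and higher, Grade 4 first, Grade 4 second and higher; febrile neutropenia Grade 3 first–second, Grade 3 third, Grade 4 any. Four of them reduce the dose: neutropenia Grade 3 second and higher (80%), Grade 4 first (80%), Grade 4 second and higher (60%), and febrile neutropenia Grade 3 first–second (60%). Footnote d is on all four. Of the three drugs it names, none is given in this trial. The talimogene laherparepvec instruction in each cell is complete without it.

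**Footnote a.** Version 3.0 appears here only. Version 5.0 appears in the synopsis and in Sections 3.2.1, 5.6, 7.0 and 9.1.2. The documents reproduce neither version, so they cannot show that any particular grade would change. The Grade 3 and Grade 4 neutropenia rows print their own count cut-offs.

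**Febrile-neutropenia overlap.** Let T be the temperature in a patient with neutropenia.

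| T | Meets Grade 3 bracket (≥38.5) | Meets Grade 4 bracket (>38.5) | Action, 1st or 2nd event | Action, 3rd event |
|---|---|---|---|---|
| exactly 38.5 °C | yes | no | hold, resume at 60% | stop |
| above 38.5 °C | yes | yes | hold and resume at 60%, **and** stop | stop |

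The Grade 4 set lies wholly inside the Grade 3 set. The conflict is confined to first and second events. If the text extraction altered one of the two signs so that both are really the same, the overlap would be complete rather than removed.

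**Effect on exposure.** Four cohort doses are planned (Table 3.1). Take a single event after cohort dose k:

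- stop: share = k / 4
- resume at 60%, recovery in time for the next dose: share = [k + 0.6 × (4 − k)] / 4
- resume at 60%, one dose missed: share = [k + 0.6 × (3 − k)] / 4, because under Section 7.1 a dose delayed by more than one week counts as missed and is not made up

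| Event after dose | Resume, none missed | Resume, one missed | Stop |
|---|---|---|---|
| 1 | (1 + 1.8)/4 = 70% | (1 + 1.2)/4 = 55% | 25% |
| 2 | (2 + 1.2)/4 = 80% | (2 + 0.6)/4 = 65% | 50% |
| 3 | (3 + 0.6)/4 = 90% | 3/4 = 75% | 75% |

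At 4×10^8 PFU with an event after dose 1 and none missed, the cohort doses sum to 2.8 × 4×10^8 = 1.12×10^9 PFU versus 4×10^8 PFU. The seroconversion dose of 4×10^6 PFU, common to both, is left out.

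**The case against.** The best reply is that the row label governs, not the bracket. Read by temperature, Grade 3 alone would mean exactly 38.5 °C, which nobody would intend. The fever threshold then looks like a qualifier shared by both rows. The Grade 3 action also refers to neutropenia resolving to grade ≤1, so neutropenia is graded in its own right. Section 5.6 has the investigator grade events by version 5.0, and an event with one assigned grade falls in one row.

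This reading is possible, but the table does not state it. In the neutropenia rows just above, the brackets for Grades 3 and 4 do define the grade. A reader who falls back on the CTCAE grade meets footnote a, which names a different version from Section 7.0. The ambiguity therefore remains, although actual divergence between sites is a possibility and has not been shown.

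Other parts of the reply stand:

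- Footnotes a and d, taken alone, change no talimogene laherparepvec instruction.
- Grade 3 and Grade 4 febrile neutropenia are both DLTs under Section 3.2.1, so DLT counts do not change.
- Section 9.1.6 plans no analysis of cumulative PFU.
- Neutropenia is listed neither in Table 1.2.1.3 (N = 292) nor in the side-effect lists of Section 7.2, so few patients are likely to be affected. Those data, however, do not come from intraperitoneal use.
- The exposure gap depends on recovery time. With one missed dose it shrinks, and after dose 3 it vanishes.

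**Conclusion.** The concern holds. All three defects stand in the operative text of the dose-modification table. Footnote d and the version citation are plain errors with no demonstrated effect on dosing or grading. The febrile-neutropenia overlap is a contradictory continue-or-stop rule for a first or second event above 38.5 °C, provided the brackets define the grade as they do in the Grade 3 and 4 neutropenia rows.

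Where the conflict arises, the difference in planned cohort dose ranges from 45 percentage points (70% versus 25%, event after dose 1, none missed) down to zero (event after dose 3, next dose missed). These figures assume one event and no further reduction. The likely number of patients is small. The point is worth correcting because the rule decides whether an individual patient continues a live virus and because the correction is simple.

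**What to change.** Amend Table 7.1 in three places:

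1. In footnote d, delete the text on oxaliplatin, capecitabine and pembrolizumab. The sentence on case report form reporting can stay.
2. In footnote a, cite version 5.0.
3. Replace the bracketed febrile-neutropenia criteria with mutually exclusive ones, for example the CTCAE version 5.0 grade alone, so that each event leads to one action.

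The clinical content of the third change is for the sponsor to decide. The cost is amendment wording only.
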